12.3.5.4.3 Skin microbiology

The incidence of skin colonisation with S. aureus will be presented by visit and treatment group for the subjects in the full analysis set. The incidence at Week 16 will be compared between the tralokinumab treatment group and the placebo group among subjects who are positive at baseline using a chi-squared test.

12.3.6 Analysis of maintenance treatment

12.3.6.1 Analysis of maintenance endpoints

For the two dichotomous maintenance endpoints, IGA 0/1 and EASI75 at Week 52, an adapted version of the primary estimand for the primary endpoints will be considered:

• Treatment difference in response rates of IGA 0/1 and EASI75 after 52 weeks achieved without rescue medication and without transfer to open-label treatment

The adapted estimand takes into account that throughout the maintenance period subjects will be actively discontinued from the treatment randomised at Week 16 and transferred to the open-label tralokinumab arm if they meet the prespecified treatment failure criteria described in Section 7.1.

This estimand assesses the expected difference in response rates (defined as response obtained without initiation of any rescue medication and without transfer to open-label treatment) after 52 weeks in patients responding to tralokinumab at Week 16 (as measured by a positive IGA 0/1 or EASI75 response), resulting from a maintenance treatment regimen with tralokinumab Q2W or tralokinumab Q4W compared to a treatment regimen with placebo.

Primary analysis for the maintenance estimand

All subjects who prior to the Week 52 visit have received rescue medication, including TCS, and/or been transferred to the open-label tralokinumab arm will be considered non-responders.

This reflects an assumption that initiation of rescue medication or transfer to open-label treatment indicates failure of the re-randomised treatment assigned at Week 16, and that a (possible) observed positive response thereafter is not attributable to the treatment received from Week 16. In addition, all subjects with missing endpoint data at Week 52 visit will be imputed as non-responders.

Trial ID: LP0162-1325	Date: 14-Aug-2018	Version: 4.0
		Page 109 of 169

The 4 hypotheses of primary interest for maintenance treatment will be tested sequentially with the next hypothesis in the sequence only being tested if the previous one was significant. The multiple testing procedure planned to control the overall type 1 error rate for the trial is described in detail in Section 12.3.4. The maintenance endpoints will be evaluated in the following order:

- No difference between Q2W and placebo for IGA 0/1 at Week 52.
- No difference between Q2W and placebo for EASI75 at Week 52.
- No difference between Q4W and placebo for IGA 0/1 at Week 52.
- No difference between Q4W and placebo for EASI75 at Week 52.

For the IGA 0/1 endpoint, the analysis will be based on the subjects in the maintenance analysis set who obtained an IGA of 0/1 at Week 16 without rescue medication. For the EASI75 endpoint, the analysis will be based on the subjects in the maintenance analysis set who obtained an EASI75 at Week 16 without rescue medication.

For each endpoint (IGA 0/1 and EASI75 at Week 52) the estimated response rates and corresponding 95% CIs, and the pairwise treatment differences will be presented. The difference in response rates between treatment groups will be analysed using the Cochran-Mantel-Haenszel test stratified by region. The null hypotheses of no difference in response rates will be tested against the two-sided alternative that there is a difference.

Sensitivity analysis for the maintenance estimand

In a sensitivity analysis, data missing at Week 52 for subjects who did not receive rescue medication, did not transfer to open-label and did not withdraw from the trial due to AE or lack of efficacy will be imputed using LOCF.

Pooled analyses across both LP0162-1325 and LP0162-1326

In order to achieve more precise estimates of clinical response within treatment groups in the maintenance period, analyses of IGA 0/1 and EASI75 at Week 52 will be performed on pooled data from the 2 trials LP0162-1325 and LP0162-1326. For each endpoint (IGA 0/1 and EASI75 at Week 52) the estimated response rates and corresponding 95% CIs and the pairwise treatment differences will be presented. The difference in response rates between treatment groups will be analysed using the Cochran-Mantel-Haenszel test stratified by region within trial. The pooled analyses will only be presented in marketing authorisation applications.

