7.2 Number of subjects needed

Assuming a screening failure rate of 25%, approximately 1040 subjects will be screened and approximately 780 subjects will be randomly assigned to trial treatment in the initial treatment period (3:1; 585 subjects in the tralokinumab arm and 195 subjects in the placebo arm). At Week 16, approximately 40% of the tralokinumab treated subjects are expected to be re-randomised (2:2:1 to tralokinumab Q2W, tralokinumab Q4W, and placebo, respectively) into the maintenance treatment period; any subject who does not achieve a clinical response at Week 16 will be treated with open-label tralokinumab Q2W.

The statistical power considerations for this sample size (n=780) are described in Section 12.1.

This trial will be conducted at approximately 130 sites in Europe, North America, and Japan. The anticipated minimum number of subjects per trial site is 4 and the maximum number of subjects is 30.

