9.3 Treatment assignment

Subjects who have been found to comply with all the inclusion criteria and not to violate any of the exclusion criteria will be randomised at baseline (Day 0) to receive treatment with either tralokinumab or placebo in the initial treatment period. Treatment assignment will be pre-planned according to a computer-generated randomisation schedule in a 3:1 ratio (tralokinumab:placebo) stratified by region (North America, Japan, and Europe) and baseline disease severity (IGA 3 or 4).

Subjects found to be eligible for maintenance treatment at Week 16 will be re-randomised to the maintenance treatment period in a 2:2:1 ratio (tralokinumab Q2W:tralokinumab Q4W:placebo) stratified by region and IGA response at Week 16 (IGA 0/1 or IGA >1).

Subjects randomised to placebo in the initial treatment period who achieve a clinical response at Week 16 (IGA 0/1 or EASI75) will continue to receive placebo Q2W in the maintenance treatment period.

Trial ID: LP0162-1325	Date: 14-Aug-2018	Version: 4.0
		Page 56 of 169

Subjects not eligible for the maintenance part of the trial will be transferred to open-label tralokinumab Q2W treatment.

IWRS will be used to control randomisation and stratification factors, along with IMP supply chain and expiry tracking.

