12.3.6.2.2 Continued treatment for non IGA responders

The number of responders according to IGA 0/1 at Week 52 will be tabulated for the subgroup of subjects in the maintenance analysis set who are re-randomised meeting the EASI75 criterion but not the IGA 0/1 criterion at Week 16.

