	The change from baseline to Week 16 in SCORAD will be analysed using a repeated measurements model on the post baseline responses up to Week 16.
	Reduction of Worst Daily Pruritus NRS weekly average of at least 4 is a binary endpoint, and as such it will be analysed as described for the primary endpoint. Change from baseline to Week 16 in DLQI will be analysed the same way as change in SCORAD.
	Maintenance endpoints
	The 4 hypotheses of primary interest for maintenance treatment will be tested sequentially with the next hypothesis in the sequence only being tested if the previous one was significant. The maintenance endpoints will be evaluated in the following order:
	• No difference between Q2W and placebo for IGA 0/1 at Week 52.
	• No difference between Q2W and placebo for EASI75 at Week 52.
	• No difference between Q4W and placebo for IGA 0/1 at Week 52.
	• No difference between Q4W and placebo for EASI75 at Week 52.
	For each endpoint (IGA 0/1 and EASI75 at Week 52) the estimated response rates and corresponding 95% CIs, and the pairwise treatment differences will be presented. The difference in response rates between treatment groups will be analysed using the Cochran Mantel-Haenszel test stratified by region.
	A multiple testing procedure to control the overall type 1 error rate for the trial will be used.

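### The confirmatory Week 52 EASI75 test omits Week 16 IGA response, a re-randomisation factor: it stays valid but is mildly conservative if that factor is prognostic

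*Protocol*

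**What the plan says.** Protocol 9.3 (likewise 7.1 and Appendix 1) re-randomises Week 16 tralokinumab responders 2:2:1 to Q2W, Q4W or placebo, "stratified by region and IGA response at Week 16 (IGA 0/1 or IGA >1").

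For the Week 52 endpoints, Protocol 12.3.6.1 states: "The difference in response rates between treatment groups will be analysed using the Cochran-Mantel-Haenszel test stratified by region". Appendix 1 repeats it: "using the Cochran Mantel-Haenszel test stratified by region". The pooled analysis with LP0162-1326 uses a "Cochran-Mantel-Haenszel test stratified by region within trial", and the exploratory log-rank test in 12.3.6.2.1 also uses region only. The supportive analysis in 12.3.6.2.3 (IGA 0/1 or EASI75 at Week 52) takes its method from 12.3.6.1. SAP 6.6 refers efficacy back to the protocol, and none of the additions listed in SAP 4 touches these strata.

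The four maintenance hypotheses are "tested sequentially with the next hypothesis in the sequence only being tested if the previous one was significant". Q2W EASI75 is second and Q4W EASI75 is last. The level is 4%, rising to 5% if all the parallel Week 16 secondary endpoints are significant (Protocol 12.3.4; SAP 6.6.1 for the US).

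By contrast, the Week 16 primary test (12.3.5.1.1) is stratified by both factors of the first randomisation.

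**The concern.** Stratified allocation balances the arms on Week 16 IGA response. If that factor predicts maintained EASI75, the balance removes a source of variation from the treatment difference. A test that ignores the factor still counts that variation in its variance, so its standard error is too large and its rejection rate under the null falls below nominal.

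This affects two of the four confirmatory maintenance hypotheses, the supportive combined endpoint and the pooled EASI75 analysis. It does not affect IGA 0/1, whose analysis set contains only subjects with Week 16 IGA 0/1. What is at stake is some precision and, in unfavourable scenarios, a little power. No false claim is made more likely.

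**Working it through.** **Inputs from Protocol 12.1 and 7.2.** 235 EASI75 responders (94/94/47); 175 IGA responders; planned Week 52 EASI75 rates of 90%/55%/5%; two-sided 4%.

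**Inputs assumed, not in the documents.** Region split 45/40/15, permuted blocks of 5, and the gap g in Week 52 EASI75 rate between the IGA strata.

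**1. The plan's own figure.** A pooled-variance normal approximation with 94 vs 47 subjects at 4% gives power above 99.99% for Q2W and for Q4W. The stated >99% is reproduced.

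**2. The IGA mix.** Protocol 7.2 says "approximately 40% of the tralokinumab treated subjects are expected to be re-randomised", which equals the assumed EASI75 rate. This implies that the IGA responders are nested in the EASI75 responders. Hence s = 175/235 = 74.5% have IGA 0/1 and 60/235 = 25.5% have IGA >1. Protocol 12.3.6.2.2 confirms that the second group exists: it tabulates subjects "who are re-randomised meeting the EASI75 criterion but not the IGA 0/1 criterion at Week 16".

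**3. Size of the region-only test under the null.** With overall rate p, the ratio of within-stratum to total variance is r = 1 − s(1−s)g²/[p(1−p)], with s(1−s) = 0.190. The size is 2[1 − Φ(2.054/√r)].

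| p, gap | r | Size, formula | Simulated, region only | Simulated, region × IGA |
|---|---|---|---|---|
| 56%, 0 | 1.000 | 4.00% | 4.00% | 4.00% |
| 56%, 15 | 0.983 | 3.83% | 3.82% | 3.99% |
| 59%, 25 | 0.951 | 3.52% | 3.44% | 3.90% |
| 60%, 40 | 0.873 | 2.80% | 2.79% | 3.98% |

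The simulations use 200,000 trials per row, Q4W vs placebo. In a separate run without stratified allocation (70% vs 30%, 75/25 mix), the region-only size is 3.9%. The shortfall therefore comes from stratifying the allocation and not the analysis.

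**4. Standard error at the planned rates.** The region-only variance is about p₁q₁/94 + p₀q₀/47. Stratifying by IGA removes 0.190(g₁²/94 + g₀²/47). The placebo gap cannot exceed 5%/0.745 = 6.7 points. For Q2W with a 30-point gap, the total is 0.09/94 + 0.0475/47 = 0.001968 and the amount removed is 0.000200. The ratio of standard errors is √(0.001968/0.001768) = 1.055 with the IGA mix held fixed. With random stratum sizes (60,000 simulated trials, Mantel-Haenszel difference with Sato variance), the excess is 1.4% to 2.9% for Q2W and 0.7% to 1.5% for Q4W at gaps of 15 to 30 points.

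**5. Power for Q4W EASI75 (Q4W 55%, gap 30 points).** The fixed-sequence columns assume three things: Week 52 IGA responders are nested in EASI75 responders, the Q2W and Q4W IGA rates are the planned 80% and 50%, and the placebo IGA rate is 50/55 of its EASI75 rate.

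| Placebo EASI75 | Region only | Region × IGA | In sequence, region only | In sequence, region × IGA |
|---|---|---|---|---|
| 5% (planned) | 100.0 | 100.0 | 99.98 | 99.98 |
| 20% | 98.63 | 98.92 | 89.15 | 89.24 |
| 25% | 93.21 | 94.36 | 74.38 | 74.74 |
| 30% | 79.65 | 81.87 | 54.54 | 55.20 |
| 40% | 34.73 | 37.44 | 17.05 | 17.77 |

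The unconditional gains are 0.3, 1.2, 2.2 and 2.7 points; in sequence they are 0.1, 0.4, 0.7 and 0.7. The in-sequence gain is smaller because the Q4W IGA test ahead of it passes in only 75.6%, 57.6% and 22.8% of trials at placebo 25%, 30% and 40%. At those placebo rates the in-sequence gain is 0.2/0.3/0.3 points if the placebo IGA-to-EASI75 ratio is 1.0, and 1.0/1.9/2.3 if it is 0.6. With a 15-point gap the gain is at most 0.6 unconditionally and 0.2 in sequence. With no gap, stratifying by IGA costs at most 0.1 point.

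**The case against.** The strongest reply is that nothing happens under the plan's own assumptions: the power gain is 0.0 points and type I error is protected. That is correct.

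Nothing in the documents says how far Week 16 IGA predicts maintained EASI75. The one structural link is narrow. Subjects who have "been transferred to the open-label tralokinumab arm will be considered non-responders", and the transfer rule needs only loss of EASI75 when Week 16 IGA is >1, but an IGA worsening as well when it is 0 or 1. This separates the strata only for subjects who lose EASI75 over three visits and regain it by Week 52. The sizes in step 3 also need null rates of 56% to 60%. Near the planned placebo rate (6% vs 2% by stratum) both tests fall short, at 3.2% and 3.3%, mainly from discreteness. Protocol 12.3.6.1 names no variance method, so the standard-error figures depend on the estimator assumed. All of this stands and limits the importance of the point.

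Sparse strata are a plausible, though unstated, reason for using region only. About 12 placebo subjects would have IGA >1, or 5.4/4.8/1.8 by region under the assumed split. A stratum with subjects in only one of the two arms (Q4W, placebo) occurs in 1.7% of simulated trials. It rises to 38% if the smallest region holds 7% and blocks are of 10, and to 3.9% to 6.5% if 10% to 25% of subjects are dropped for rescue use before Week 16. On average, fewer than one subject is set aside, and the gain remains.

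Region only is also applied consistently across the maintenance section. The SAP (20 May 2019) postdates the data cut-off (11 April 2019). In Japan these are primary maintenance endpoints (Protocol 6.2, Appendix 7). These are reasons to document any change carefully, not reasons to leave the mismatch unexplained.

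**Conclusion.** The mismatch is real and confined to the analyses that mix IGA strata: the EASI75 test at Week 52, the supportive combined endpoint and the pooled EASI75 analysis. The region-only test is valid. It is conservative only to the extent that Week 16 IGA is prognostic, and mildly so for gaps of 15 to 25 points. At planned rates, the only visible effect is a standard error up to 2.9% too large for gaps up to 30 points. Power differs by more than a few tenths of a point only with a gap near 30 points and placebo maintenance of 25% or more, against 5% planned. These sizes rest on the assumed gaps, region split and block size; the direction does not. The point is low priority, but the correction costs almost nothing and follows the trial's own practice at Week 16.

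**What to change.** Before the code is broken, state in the SAP that the Week 52 EASI75 test and the supportive IGA 0/1 or EASI75 test are stratified by region and Week 16 IGA response (0/1 vs >1). Keep region only for IGA 0/1, and report the region-only EASI75 test as a sensitivity analysis. State how strata with subjects in only one arm are handled. Align the pooled EASI75 test (region × Week 16 IGA within trial) if LP0162-1326 re-randomised by the same factors, which these documents do not show.

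At a minimum, give the reason for leaving IGA out and pre-specify the region × IGA test as a sensitivity analysis.

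No new data are needed, since both factors are held in the IWRS. The cost is a justified change to a pre-specified confirmatory test, documented as Protocol 12.3.10 requires, and about 0.1 point of power if Week 16 IGA turns out not to be prognostic.

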12.3.6.2 Analysis of other maintenance endpoints

12.3.6.2.1 Time to relapse

The following 2 types of relapse will be considered and analysed:

- Relapse according to IGA: first assessment of an IGA≥2 or initiation of rescue medication after initiation of maintenance treatment among subjects in the maintenance analysis set who obtained an IGA 0/1 at Week 16 without rescue medication.
- Relapse according to EASI75: first time of not achieving EASI75 or initiation of rescue medication after initiation of maintenance treatment among subjects in the maintenance analysis set who obtained EASI75 at Week 16 without rescue medication.

Kaplan-Meier curves of time to relapse will be estimated and presented by treatment for the maintenance analysis set. In a supplementary exploratory analysis, tralokinumab Q2W vs. placebo and tralokinumab Q4W vs. placebo will be compared using a log-rank test stratified by region.

Subjects leaving the trial without meeting the relapse criteria will be censored at the date of the last assessment visit.

12.3.6.2.2 Continued treatment for non IGA responders

The number of responders according to IGA 0/1 at Week 52 will be tabulated for the subgroup of subjects in the maintenance analysis set who are re-randomised meeting the EASI75 criterion but not the IGA 0/1 criterion at Week 16.

12.3.6.2.3 Supportive maintenance

To support the maintenance objective, the response IGA 0/1 or EASI75 at Week 52 will be presented and analysed as described above for the primary analysis of the maintenance estimand for subjects in the maintenance analysis set who did not receive rescue medication prior to Week 16.

12.3.7 Analysis of safety

The analyses of safety will be based on the safety analysis sets. The reporting of safety data will be presented separately for the initial treatment, the maintenance treatment, and the open-label treatment.

12.3.7.1 Adverse events

AEs will be coded during the course of the trial according to Medical Dictionary for Regulatory Activities (MedDRA). AEs will be presented by preferred terms and primary system organ class (SOC).

Treatment-emergent AEs will be summarised, however, all AEs recorded during the course of the trial will be included in the subject data listings. An event will be considered treatment-emergent if started after the first use of IMP or if started before the first use of IMP (applicable if subject had a wash-out) and worsened in severity thereafter. The tabulations described in the following will only include the treatment-emergent events. In each of the tabulations, AEs will be defined by MedDRA preferred terms within primary SOC.

An overall summary of the number of treatment-emergent AEs, number (percentage) of subjects with any treatment-emergent AEs, SAEs, deaths, premature discontinuations from the trial due to AEs, treatment-related AEs and severe AEs will be presented.

The number of AEs and the number of subjects experiencing each type of AE will be tabulated by treatment group. The percentage of subjects with AEs in the initial treatment period will be compared between treatment groups by a chi-square test or Fisher's exact test (if expected cell count < 5).

The severity for each type of AE will be tabulated by treatment group.

The causal relationship to IMP for each type of AE will be tabulated by treatment group.

Related AEs are defined as AEs for which the investigator has not described the causal relationship to IMP as 'not related'. The number of related AEs and the number of subjects experiencing each type of related AE will be tabulated. The percentage of subjects with related AEs in the initial treatment period will be compared between treatment groups by a chi-square test or Fisher's exact test (if expected cell count <5).

SAEs and AESIs will be evaluated separately. A narrative for each SAE will be given. AESIs and AEs leading to withdrawal from trial will be tabulated and listed.

